8.9.2 Clinical Laboratory Parameters

Descriptive statistics for clinical laboratory values (in SI units) and changes from study baseline values at each assessment time point will be presented by treatment sequence for clinical laboratory parameters specified in the protocol. Change from period baseline by treatment and treatment week during DB period will also be presented.

The clinical laboratory parameters include the following:

- Chemistry: Alanine aminotransferase (ALT), Alkaline phosphatase, Aspartate aminotransferase (AST), Bilirubin (total), Blood urea nitrogen (BUN), Calcium, Chloride, Serum creatinine, Gamma-glutamyl transpeptidase (GGT), Serum glucose, Potassium, Protein (albumin and total), Sodium, Creatine Kinase
- Hematology: Hematocrit, Hemoglobin, Platelet count, Red blood cell (RBC) count, White blood cell (WBC) count
- Urinalysis: Appearance, Color, pH, Specific gravity, Ketones, Protein, Glucose, Pregnancy test (if applicable)
- Ketosis Detection: Betahydroxybutyrate (BHB)
- Lipid Profile: Low-density lipoprotein (LDL), High-density lipoprotein (HDL), Triglycerides, Total cholesterol

The frequency and percentage of subjects who experience abnormal clinical laboratory results (i.e. outside of reference ranges) and/or clinically significant abnormalities (as determined by the Investigator) after study drug administration will be presented for each clinical laboratory measurement by treatment sequence and period.

Hy's Law criteria will be applied against test results. Subjects with serum total bilirubin $>2 \times \text{ULN}$ and alanine aminotransferase (ALT) or aspartate aminotransferase (AST) $>3 \times \text{ULN}$ will be considered positive for Hy's law status. Shift tables will be produced by treatment sequence:

- Hy's Law negative at study baseline, remaining Hy's Law negative throughout the DB treatment period

- Hy's Law negative at study baseline, becoming Hy's Law positive at any point during the DB treatment period
- Hy's Law positive at study baseline and Hy's Law negative throughout the DB treatment period
- Hy's Law positive at study baseline and Hy's Law positive at any point during the DB treatment period
- Hy's Law negative at study baseline, remaining Hy's Law negative throughout the study
- Hy's Law negative at study baseline, becoming Hy's Law positive at any point during the study
- Hy's Law positive at study baseline and Hy's Law negative throughout the study
- Hy's Law positive at study baseline and Hy's Law positive at any point during the study

A data listing of all subjects who are Hy's Law positive will be produced.

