### 7.3.2 Exclusion Criteria

Individuals who meet any of the following exclusion criteria will not be eligible to participate in the study:

1. Any known hypersensitivity to triheptanoin or safflower oil that, in the judgment of the Investigator, places the subject at increased risk for adverse effects
2. Prior use of triheptanoin within 30 days prior to Screening
3. History of, or current suicidal ideation, behavior and/or attempts per C-CSSRS at Screening or Baseline
4. Pregnant and/or breastfeeding an infant at Screening or Baseline
5. Participants unwilling or unable to discontinue use of a prohibited medication or other substance that may confound study objectives (Section 7.4.6.1 [MCT oil, barbiturates, pancreatic lipase inhibitors, KetoCal or other KD supplements, and/or KD])
6. Glut1 DS treatment regimen, including AEDs, should be stable for at least 30 days prior to Screening
7. Use of any investigational product (drug, medical food, or supplement, including medium chain triglyceride [MCT] oil, including coconut oil) within 30 days prior to Screening
8. Has a concurrent disease or condition, or laboratory abnormality that, in the view of the Investigator, places the subject at high risk of poor treatment compliance or of not completing the study, or would interfere with study participation or introduces additional safety concerns
9. Feeding or nutrition that, in the opinion of the dietitian, potentially affects consistent administration of study drug

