### **7.6.3.3 Safety Analyses**

All AEs will be coded using the Medical Dictionary for Regulatory Activities (MedDRA). The incidence and frequency of AEs will be summarized by System Organ Class, Preferred Term (PT), relationship to study drug, and severity. All reported AEs with onset during the treatment (i.e. treatment-emergent AEs) will be included in the analysis. For each AE, the percentage of subjects who experienced at least 1 occurrence of the given event will be summarized by treatment group. The numbers (frequency) and incidence rates of AEs and SAEs will be summarized during exposure to study drug during the double-blind period, and also throughout the study including the open-label period. Special attention will be given to those subjects who died, discontinued treatment due to an AE, or experienced a SAE (e.g., summaries, listings, and narrative preparation may be provided, as appropriate).

Clinical laboratory data will be summarized by the type of laboratory test. Reference ranges will be used in the summary of laboratory data. The frequency and percentage of subjects who experience abnormal clinical laboratory results (i.e. outside of reference ranges) and/or

clinically significant abnormalities (as determined by the Investigator) will be presented for each clinical laboratory measurement. For C-SSRS, the percentage of subjects reporting any treatment emergent suicidal ideation and any treatment emergent suicidal behavior will be summarized descriptively by treatment group and visit week, respectively. The SAP will provide additional details on the planned safety analyses.

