5.5 Baseline

- Movement Disorder:

Study baseline for movement disorder frequency as recorded by the subject/caregiver in diary will be normalized to a 4-week rate as

$$\frac{\text{total number of movement disorder events during the 6 weeks run-in period} \times 28}{\text{number of days with diary data during the 6 weeks run-in period}}$$

Study baseline for total duration of movement disorder in hours will be normalized to a 4-week rate as

$$\frac{\text{total duration of movement disorders in hours during the 6 weeks run-in period} \times 28}{\text{number of days with diary data during the 6 weeks run-in period}}$$

- For other efficacy endpoints, study baseline is defined as the last non-missing assessment prior to or on the date of the first dose of investigational product
- For safety endpoints, study baseline is defined as the last non-missing assessment prior to or on the date of the first dose of investigational product

Period baseline is defined as the last non-missing assessment prior to or on the date of the first dose of investigational product for each DB treatment period. A value from the first treatment period will not be considered as the period baseline for the second treatment period.

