8.9 Safety Analyses

All safety analyses will be performed using the Safety Analysis Set. Safety parameters will include AEs, clinical laboratory parameters, vital signs, ECG parameters, and other safety parameters. No statistical comparisons will be performed.

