8.9.1 Adverse Events

Adverse events will be coded by SOC and PT using the Medical Dictionary for Regulatory Activities (MedDRA). AEs during Run-In period will be summarized.

A treatment emergent adverse event (TEAE) will be considered and assigned to the treatment group (UX007 or Placebo) if the AE (classified by preferred term) start date occurs or worsens in severity on or after the first dose of study drug in the corresponding treatment period and before the first dose of study drug in the next treatment period. For example, an AE will be assigned to the treatment in Treatment Period I if it occurred during the wash out period. An AE that occurs within 30 days after the last dose of study drug in the last treatment period will be assigned to the last treatment period.

The incidence of subjects reporting TEAEs in each treatment and treatment sequence will be tabulated by SOC and PT; by SOC, PT, and severity; and by SOC, PT, and relationship to study drug. If more than one event occurs with the same preferred term for the same subject, the subject will be counted only once for that preferred term using the most severe and most related occurrence for the summarizations by severity and by relationship to the study drug.

The incidence of subjects reporting TEAEs by treatment and treatment period will also be summarized by SOC and PT for each of the following categories:

- All TEAEs
- Treatment related TEAEs
- Grade 3 or 4 TEAEs
- Serious TEAEs
- Serious and related TEAEs
- TEAEs leading to study discontinuation
- TEAEs leading to treatment discontinuation

- TEAEs leading to death

Exposure adjusted TEAE incidence is defined as total number of occurrences of an event summed across all subjects by treatment divided by the total exposure duration. A TEAE which occurred during the wash-out period will be considered and counted into the first treatment period. Exposure adjusted TEAE incidence will be summarize by treatment, and period.

Detailed listings for all AEs, TEAEs, serious TEAEs, AEs leading to study/treatment discontinuation, and death will also be generated.

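### The laboratory abnormality table in SAP 8.9.2 mixes pre-existing with new abnormalities; a shift table from baseline would separate them (minor)

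*SAP*

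**What the plan says.** SAP 8.9.2 defines the categorical laboratory table as "The frequency and percentage of subjects who experience abnormal clinical laboratory results (i.e. outside of reference ranges) and/or clinically significant abnormalities", and the sentence goes on: "after study drug administration will be presented for each clinical laboratory measurement by treatment sequence and period". Protocol 7.6.3.3 plans the same table ("The frequency and percentage of subjects who experience abnormal clinical laboratory results (i.e. outside of reference ranges) and/or") with no baseline condition, so the two documents agree.

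Elsewhere the SAP does take account of status before dosing:

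- **Adverse events (SAP 8.9.1).** An event is treatment-emergent if its "start date occurs or worsens in severity on or after the first dose of study drug in the corresponding treatment period".
- **Hy's Law (SAP 8.9.2).** The rows are conditioned on baseline, for example Hy's "Law negative at study baseline, becoming" positive.
- **Baseline definitions (SAP 5.5).** A study baseline and a period baseline are both defined. For the latter, "A value from the first treatment period will not be considered as the period baseline for the second treatment period".

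Safety output is descriptive. SAP 8.9 states: "No statistical comparisons will be performed".

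**The concern.** Protocol 6.1.4 frames the laboratory safety endpoint as clinically significant change, whereas this table describes status after dosing. Eligibility does not require normal laboratory values. Exclusion criterion 8 removes a subject only if he or she "Has a concurrent disease or condition, or laboratory abnormality that, in the view of the Investigator, places the subject at high risk" of poor compliance or non-completion, or if study participation or safety would be affected. Some subjects can therefore enter with out-of-range values.

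Two features of the trial make the distinction useful. In the crossover, an abnormality that arises in Period I and outlasts the washout is counted again in Period II under the other treatment. In the extension, UX007 is given for up to three years at a target of about 30% of caloric intake, with no placebo. The table's wording is not limited to the double-blind phase, and in the extension nothing in it shows how many of the abnormal subjects were abnormal before any drug.

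**Working it through.** **Step 1. Does another planned output fill the gap?** The table below sets the laboratory outputs side by side.

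| Output | Categorical | Referenced to baseline | Attributable to treatment |
|---|---|---|---|
| Out-of-range or clinically significant count (SAP 8.9.2) | Yes | No | Yes, through sequence and period |
| Change from study baseline (SAP 8.9.2) | No | Yes | By sequence and time point |
| Change from period baseline (SAP 8.9.2) | No | Yes | Yes |
| Hy's Law shifts (SAP 8.9.2) | Yes | Yes, study baseline | No: by sequence, over the whole double-blind period or whole study |
| Treatment-emergent adverse events (SAP 8.9.1; protocol 7.5.4.5, 7.5.4.10) | Yes | Yes | Yes, but only changes judged clinically significant |

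SAP 7.4 mentions shift tables, but only to say which records enter them; it creates none for individual analytes. For routine analytes, no output is categorical, baseline-referenced and attributable to treatment unless the investigator judged the change clinically significant.

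**Step 2. How much mixing could there be?** The plan gives no figure to reproduce and no rates, so all inputs here are assumptions for a single analyte:

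- b = share out of range before dosing
- s = share of those still out of range after dosing
- i = share newly out of range among those normal before dosing

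Share of subjects counted = b·s + (1 − b)·i. Pre-existing share of that count = b·s / [b·s + (1 − b)·i].

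| b | s | i | Counted | Already abnormal before dosing |
|---|---|---|---|---|
| 5% | 0.5 | 10% | 0.025 + 0.095 = 12.0% | 21% |
| 5% | 0.5 | 5% | 0.025 + 0.0475 = 7.3% | 34% |
| 10% | 0.8 | 10% | 0.08 + 0.09 = 17.0% | 47% |
| 10% | 0.8 | 5% | 0.08 + 0.045 = 12.5% | 64% |
| 30% | 0.8 | 5% | 0.24 + 0.035 = 27.5% | 87% |

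The planned layout has double-blind cells of about 20 subjects (40 subjects, two sequences). In such a cell the fourth row means 20 × 0.125 = 2.5 counted, of whom 20 × 0.08 = 1.6 are pre-existing and 20 × 0.045 = 0.9 are new. For an analyte that is never abnormal at entry (b = 0) the pre-existing share is zero.

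**Step 3. Does persistence from Period I have a predictable direction?** Let qT and qP be the emergence rates on UX007 and placebo, and rT and rP the shares of Period I abnormalities from each that are still present in Period II. Those that resolve are at risk again. Among subjects normal at entry, summing each treatment over its two cells gives a UX007-minus-placebo difference proportional to

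D = 2(qT − qP) + rP·qP(1 − qT) − rT·qT(1 − qP).

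Take qT = 0.15 and qP = 0.05, both assumed:

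- rT = rP = 0: D = 0.20.
- rT = rP = 0.5: D = 0.20 + 0.02125 − 0.07125 = 0.15, a fall of 25%.
- rT = 0, rP = 0.5: D = 0.20 + 0.02125 = 0.221, a rise of about 11%.

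So carry-over can move the contrast either way.

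**The case against.** The strongest reply is that this is not an error. Protocol and SAP agree, and neither calls the table treatment-emergent; it is described as abnormal results after study drug. That stands, and the point is an improvement to a shared choice rather than a departure by the SAP.

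The second reply is that the remaining gap is narrow. Change from period baseline is summarised by treatment with quartiles, minimum and maximum (SAP 8.1), so extreme changes show. Clinically significant changes become adverse events, raw data are listed, and the monitoring committee reviews unblinded safety data (protocol 7.6.6). This largely stands. A summary of changes, however, does not say how many subjects crossed a reference limit.

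A reader might go further and infer that the table systematically understates a UX007 effect, by diluting a UX007-to-placebo ratio or shrinking the excess count. The documents do not support this:

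- The SAP presents cells by sequence and period and plans no pooled ratio or pooled excess.
- Period I is a parallel comparison free of carry-over, although pre-dose abnormalities remain in its counts.
- A fixed shrinkage through carry-over needs equal persistence under both treatments. Step 3 shows the direction reversing if drug-related abnormalities resolve off drug while incidental ones persist.
- No rate in any such calculation comes from the documents.

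Nor does the table report only pre-existing abnormalities. It counts old and new together.

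**Conclusion.** The point holds as a minor one. The lack of a baseline condition follows directly from the text and rests on no assumption. How many counted subjects are pre-existing cases cannot be determined: the 21% to 87% range belongs to the assumed grid and could be lower for analytes that are rarely abnormal at entry. Pre-existing abnormalities tend to appear under both treatments, because each subject is planned to receive both, so they blur the picture without an inherent lean towards either arm. The practical loss is greatest in the extension. Efficacy conclusions are unaffected.

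**What to change.** Keep the existing table and add to SAP 8.9.2:

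- **Double-blind shift table.** For the 25 quantitative blood analytes (15 chemistry, 5 hematology, BHB, 4 lipids), show low/normal/high from period baseline to the post-dose value, by treatment and period. For lipids, name Week 0 as the baseline: they are not drawn at Week 12, and SAP 5.5 rules out Week 10.
- **Newly high and newly low counts.** Use as denominator the subjects not already abnormal in that direction.
- **Open-label version.** Give the same table against study baseline.
- **Footnote on fasting.** Under protocol 7.5.4.5, adults fast before Weeks 0, 10 and 22 but need not before Week 12. Period II shifts in glucose and BHB may therefore partly reflect fasting status.

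No new data are needed: samples are already taken at each scheduled clinic visit and analysed centrally, and reference ranges are already in use. The cost is SAP wording and a few descriptive tables.

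There are limits. At-risk denominators shrink: a cell of 20 becomes 20 × 0.95 = 19 at b = 5% and 20 × 0.70 = 14 at b = 30%, with further loss in Period II where abnormalities persist. For lipids, a Week 0 baseline cannot remove Period I carry-over. Open-label shifts from study baseline would still count an abnormality that first arose on placebo. With one scheduled end-of-treatment draw per double-blind period, the shift table also partly overlaps the change-from-period-baseline summary.

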3.3 Study Duration

Subject participation during the DB Treatment Period (including the Run-in Period, Baseline, Treatment Period I, Washout, and Treatment Period II) will be 28 weeks in duration; the OLE Period allows patients to receive UX007 for up to 3 additional years, or until one of the following occurs: the subject withdraws consent, the subject is discontinued from the study at the discretion of the Investigator or Ultragenyx, the study is terminated, or until commercial availability of the study drug in the subject's region, which occurs first. The total treatment duration enables a long-term assessment of the efficacy and safety of UX007 in Glut1 DS subjects with movement disorders. A safety follow-up phone call will be conducted 30-35 days after the last dose of UX007G-CL301 study drug. The last subject's safety follow-up phone call is the defined end-of-study time point.

The schedule of assessments is shown in Section 10.2 Appendix B and Section 10.3 Appendix C.

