3.4 Randomization and Stratification Factors

Eligible subjects will be enrolled in the study and sequentially assigned an identification number. Subjects will be randomized in a 1:1 ratio to UX007/Placebo or Placebo/UX007 treatment sequence via an Interactive Web Randomization System (IWRS) based on a randomization schedule developed by an independent third-party vendor to maintain blinding. The randomization procedure will be performed without stratification.

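### The planned Hy's Law shift tables are by treatment sequence only, so the one summary of the joint criterion cannot show whether a double-blind case arose on UX007 or placebo

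*SAP*

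**What the plan says.** SAP 8.9.2 calls a subject Hy's Law positive when total bilirubin exceeds 2 times the upper limit of normal and ALT or AST exceeds 3 times. Of the display it says: "Shift tables will be produced by treatment sequence". Four rows cover the double-blind period and four cover the whole study. The rows that carry new cases are "Hy's Law negative at study baseline, becoming Hy's Law positive at any point during the DB treatment period" and "Hy's Law negative at study baseline, becoming Hy's Law positive at any point during the study". All rows start from study baseline; none uses period baseline, period or treatment.

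SAP 3.4 defines the columns: "Subjects will be randomized in a 1:1 ratio to UX007/Placebo or Placebo/UX007 treatment sequence". SAP 3.3 gives the span as "DB Treatment Period (including the Run-in Period, Baseline, Treatment Period I, Washout, and Treatment Period II", so it takes in both treatment periods and the washout.

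Elsewhere the plan splits safety data more finely:
- SAP 8.9.2, laboratory changes: "Change from period baseline by treatment and treatment week during DB period will also be presented".
- SAP 8.9.2, abnormal results: each analyte by sequence and period.
- SAP 8.9.1, treatment-emergent adverse events: assigned to UX007 or placebo, with a washout rule under which "an AE will be assigned to the treatment in Treatment Period I if it occurred during the wash out period".
- Protocol 7.6.2: safety subjects are grouped by the treatment they actually received.

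SAP 8.9.2 also promises a listing of all Hy's Law positive subjects, without specifying its columns.

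**The concern.** In a two-period crossover, sequence identifies treatment only when it is combined with period or visit. The Hy's Law rows drop that second element. A subject in the UX007/placebo column who becomes positive may have done so in Period I on UX007, in the washout, or in Period II on placebo, and all three land in the same cell. The other column has the same ambiguity in reverse order. The whole-study rows add open-label UX007 to both columns.

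A Hy's Law summary is read to see whether combined bilirubin and transaminase elevations occur on drug. Separate counts for ALT, AST and bilirubin cannot be recombined into the joint criterion, so no other planned summary table fills this gap.

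**Working it through.** The plan states no figure on this point, so there is none to reproduce. The check is whether the table can tell drug from placebo.

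**Inputs**
- Columns: UX007/placebo and placebo/UX007, allocated 1:1 (SAP 3.4).
- Planned size: 40 subjects, 20 per sequence, with 15% discontinuation projected (SAP 3.6).
- Per-period risks of becoming positive, pU on UX007 and pP on placebo: not in the documents. Values of 0% to 10% are assumed.

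**Formula.** Take completers who are negative at baseline, with independent periods and risks that depend only on treatment. In both sequences,

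P(positive at any point) = 1 − (1 − pU)(1 − pP).

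Swapping pU and pP leaves this unchanged. Expected cases per column are 20 times this probability. By treatment at onset they are 40·pU and 40·pP, since all 40 completers take each treatment once.

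| pU | pP | UX007/placebo column | placebo/UX007 column | Onset on UX007 | Onset on placebo |
|---|---|---|---|---|---|
| 5% | 0% | 1.0 | 1.0 | 2.0 | 0 |
| 0% | 5% | 1.0 | 1.0 | 0 | 2.0 |
| 2.5% | 2.5% | 0.988 | 0.988 | 1.0 | 1.0 |
| 10% | 0% | 2.0 | 2.0 | 4.0 | 0 |
| 0% | 10% | 2.0 | 2.0 | 0 | 4.0 |

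For the first row: 20 × [1 − 0.95 × 1] = 20 × 0.05 = 1.0, and 40 × 0.05 = 2.0. The first two rows describe opposite drug effects and give the same planned table.

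**Dropout.** Suppose, as an illustration, that the full 15% in each sequence leave after Period I, unrelated to liver status. Then 20 × 0.85 = 17 enter Period II. With pU = 5% and pP = 0%, the columns expect 20 × 0.05 = 1.0 and 17 × 0.05 = 0.85. With the risks swapped they expect 0.85 and 1.0. The columns now differ by 0.15 of a case, too little to read anything from.

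**Whole-study rows.** For subjects negative at baseline, the whole-study new-positive count minus the double-blind one gives cases that first appear after the double-blind period. Extension cases can thus be obtained by subtraction, but the table does not show them.

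**The case against.** The strongest reply is that attribution is available elsewhere, and this stands.
- Protocol 7.5.4.5 and 7.5.4.10 require clinically significant laboratory changes to be recorded as adverse events, and SAP 8.9.1 tabulates those by treatment. A joint elevation that the investigator judged clinically significant would appear there.
- Abnormal ALT, AST and bilirubin are shown by sequence and period, which identifies treatment.
- Positive subjects are listed. Scheduled double-blind laboratory draws fall only at Weeks 0, 10, 12 and 22, so a dated case is easily placed in a period.
- The data monitoring committee reviews unblinded safety data (Protocol 7.6.6).

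What these routes do not give is a by-treatment summary of the joint criterion. The adverse event route depends on investigator judgement, and the abnormality tables take one analyte at a time.

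A reader might infer that the table would look balanced whatever the drug does. The documents do not support that. Equality holds only in expectation and for completers. The Safety Analysis Set needs only one dose, so some subjects may receive one treatment only. With few cases the observed counts will often differ: a single case gives 1 versus 0. The new-positive rows still display every new case. The valid point is narrower: neither balance nor imbalance between these columns is a drug-versus-placebo comparison. SAP 8.9 rules out statistical comparisons of safety data, but a descriptive table still needs columns that can be interpreted.

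A reader might also take this to be the trial's main liver-safety table. The SAP gives it no such rank.

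**Conclusion.** The point holds as a presentation gap of minor severity. As specified, the Hy's Law shift tables cannot attribute a double-blind case to UX007 or placebo, and they are the only planned summary of the joint criterion. The size is best stated as non-identifiability: swapping the two treatment risks leaves expected counts unchanged, at 1.0 versus 1.0 for an assumed 5% risk on one treatment and 2.0 versus 2.0 for 10%. That rests on completers, independent periods and no period or carryover effect. The risks are illustrative.

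It would be wrong to conclude that hepatic attribution is lost from the report. The data are collected and other outputs carry the information. No efficacy inference, alpha or power is affected.

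**What to change.** In SAP 8.9.2, produce the double-blind Hy's Law shift table by treatment received (UX007 versus placebo), relative to period baseline. Alternatively, split each existing row by period within sequence, which is simpler to program and also identifies treatment.

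Either version needs an explicit rule for the Week 12 sample. Under SAP 5.5 and Table 2, that sample can serve as the Period II baseline, including when it is drawn on the day of the first Period II dose. Under the date rule in SAP 8.9.1, a finding on that day would fall in Period II. Left unstated, the same positive sample could be both a Period II baseline and a Period II case. State that a Week 12 sample taken before the first Period II dose counts as a post-baseline result of the Period I treatment and also serves as the Period II baseline. A subject already positive at Week 12 is then not counted as a new Period II case.

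Show open-label extension cases separately, and keep the by-sequence table as a supplement.

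The cost is SAP wording and one re-programmed table from data already collected. No assessment or clinical rule changes. This is a free improvement.
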